7.2.2 Expansion Cohorts

Patients are evaluable for the assessment of response in the expansion cohorts if they were dosed and have a baseline RECIST assessment. In addition, for the purposes of decision making on the expansion cohorts, a patient's T790M status must have also been identified via central testing and match the cohort expansion population under assessment (i.e. T790M+).

7.2.2.1 $\geq 2^{nd}$ line and 1^{st} line cohorts

Cohort expansion will be in patients whose NSCLC has progressed following therapy with an EGFR TKI agent and whose tumour status is T790M+. Data from these cohorts will provide a preliminary assessment of anti-tumour activity based on ORR (providing an acceptable false-negative risk of concluding that there is no activity if the true response rate is at least 30%).

A conclusion of no evidence of activity will be reached if no objective RECIST responses (confirmed PR or CR) are observed. If the true response rate is \geq 30%, the chance of observing no responses in 30 evaluable patients is <1%.

In the case that anti tumour activity, in the form of responses, is observed, 30 evaluable patients will provide reasonable confidence of estimating what the true response rate would be in this population as well as in the $\geq 2^{nd}$ line T790M- population and a 1st line population of EGFR TKI treatment-naive patients with EGFRm+ advanced NSCLC. Confidence intervals will be constructed (using the Clopper-Pearson interval) around the response rates observed in each population to enable decisions to be made about the likely success of future studies in each of the populations. For example:

•	17% ORR (5/30 responses);	80% CI [8%, 29%]
•	30% ORR (9/30 responses);	80% CI [19%, 43%]
•	50% ORR (15/30 responses);	80% CI [37%, 63%]
•	70% ORR (21/30 responses);	80% CI [57%, 81%]

In the event that there is little evidence of anti tumour activity being observed within the cohort expansions, individual cohorts may be closed prior to 30 evaluable patients being recruited. This will avoid exposing patients to a potentially ineffective therapy, providing the evidence of no anti tumour activity is strong enough at that time. For example, if 8 evaluable

patients are recruited to a cohort, and no responses are observed, it may be appropriate to conclude no evidence of activity because if the true response was \geq 30%, the chance of observing no responses in 8 evaluable patients is <6%.

If an individual cohort expansion is terminated prior to the full 30 evaluable patients being recruited, other cohorts within the expansion will still be able to complete recruitment as planned if it is deemed appropriate to do so. Any such decision will be at the discretion of AstraZeneca.

7.2.3 Paired Biopsy Cohort

Patients are evaluable for the paired biopsy cohort if they have provided at a minimum the pre-study tumour biopsy and one tumour biopsy on study treatment. The number of patients has been based on the desire to obtain adequate data whilst exposing as few patients as possible to the study procedures.

There are currently no data available, which adequately characterise or describe the variability of the biomarkers of interest in this subject population, thus the sample size cannot be calculated with consideration to statistical power. Data from 12 evaluable subjects is considered to be adequate to allow a preliminary investigation of the objectives of this study (Julious 2005).

7.2.4 Phase II Extension Cohort

The primary endpoint of the extension phase is ORR. The extension will recruit approximately 175 patients with T790M mutation positive advanced NSCLC, whose disease has progressed following either one prior therapy with an EGFR-TKI (chemotherapy-naïve, n=50) or following treatment with both EGFR-TKI and other anti-cancer therapy (n=125). With 175 patients the precision of the estimation of ORR in the overall study population will be within +/-8% (e.g. ORR 40%, 95% CI 33.0%, 47.4%). The precision of the estimation of ORR will be within +/-13% in the 50 patient cohort who have only received previous TKI treatment and within +/-9% in the 125 patient cohort who have received previous TKI treatment and other anti-cancer therapy. The study will also provide an adequate number of patients in which to assess the safety and tolerability of AZD9291; if zero events are observed in the 175 patients, there is 95% confidence that the true event rate is less than 2.2%.

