For the expansion cohorts, the summaries will be by dose and centrally confirmed T790M status (positive, negative, unknown). First line cohort(s) will be summarised separately to pre-treated cohorts. A sensitivity analysis may be performed using local T790M status for patients whose central T790M status is not available.

For the extension cohort, all summaries will be presented as a cohort and by previous treatment cohort (TKI only or TKI plus additional treatments).. For the primary objective all RECIST outcomes will be based on the independent central review, and ORR will be summarised for the patients who have measurable disease at baseline as defined by ICR.

Tumour response data will be listed and summarised by dose group, and if appropriate using the following response categories: Complete Response (CR), Partial Response (PR), Stable Disease (SD), Progressive Disease (PD) and Non-Evaluable (NE).

Objective tumour response rates will be presented together with 80% and 95% confidence intervals (calculated using the Clopper-Pearson interval), where appropriate.

Duration of response

For the expansion and extension cohorts duration of response in responding patients will be summarised and the number (%) of responding patients with a duration of response >3; >6; >9; >12 months will be presented. A Kaplan Meier plot and median duration of response with 95% CI (calculated from the Kaplan Meier plot) will be presented. DCR will be summarised with 95% confidence intervals.

Progression free survival and overall survival

The analysis population for progression free survival and overall survival will be the safety population.

PFS will be summarised for the expansion phase and the extension phase. OS will be summarised for the extension phase only.

PFS and OS will be displayed using Kaplan Meier plots. The number of events, median (calculated from the Kaplan Meier plot), and proportion of patients without an event at 6, 12 and 18 months will be summarised.

As appropriate, summaries of the number and percentage of patients who have died, are still in survival follow-up, are lost to follow-up and have withdrawn consent will be presented.

Sensitivity analysis:

The same methods of analysis will be applied to analyse ORR, DoR, DCR, tumour shrinkage and PFS based on the RECIST data assessed by the Investigator

Change in tumour size

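### Section 7.2.4 states ORR precision from a Wilson-type interval, while Section 7.9 plans Clopper-Pearson; for the 50-patient group the planned interval gives about +/-15%, not +/-13%

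*Protocol*

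**What the plan says.** Protocol Section 7.2.4 makes ORR the primary endpoint of the extension: "The extension will recruit approximately 175 patients with T790M mutation positive advanced NSCLC". They fall into two prior-treatment groups: "one prior therapy with an EGFR-TKI (chemotherapy-naïve, n=50") and "following treatment with both EGFR-TKI and other anti-cancer therapy (n=125").

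The section then gives three precision statements and one worked interval:

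- 175 patients: "the precision of the estimation of ORR in the overall study population will be within +/-8"%, with the example "e.g. ORR 40%, 95% CI 33.0%, 47.4"%.
- 50 patients: "The precision of the estimation of ORR will be within +/-13% in the 50 patient cohort".
- 125 patients: within +/-9%.

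It adds that, with no events in 175 patients, "there is 95% confidence that the true event rate is less than 2.2"%. No interval method is named in the section.

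Section 7.9, under Tumour response, says that response rates will be shown with "80% and 95% confidence intervals (calculated using the Clopper-Pearson interval"), where appropriate. It also has the extension summarised both as a whole and by previous treatment (TKI only, or TKI plus additional treatments).

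**The concern.** Section 3.2 sends the reader to Section 7.2 for the statistical justification of the extension's size. That justification contains no hypothesis test and no power calculation. It rests on the precision of ORR, together with the zero-event safety statement. The precision figures should therefore describe the interval that will be reported.

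The worked example does not match Clopper-Pearson, and +/-13% looks too tight for 50 patients under a conservative exact method. If so, the interval reported for the chemotherapy-naive group will be visibly wider than the protocol leads its readers to expect, unless the observed rate is well away from 50%.

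**Working it through.** **Inputs.** Group sizes of 175, 50 and 125, the illustrative ORR of 40% and the 95% level come from Section 7.2.4. The Clopper-Pearson method comes from Section 7.9. At 40% the responder counts are 70/175, 20/50 and 50/125.

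**Step 1: reproduce the plan's figures.** The Wilson interval, with z = 1.96, is

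centre = (p + z²/2n) / (1 + z²/n)

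half-width = z·√[p(1−p)/n + z²/4n²] / (1 + z²/n)

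- n = 175, p = 0.40: centre = 0.41098/1.02195 = 0.4021; half-width = 1.96 × √(0.0013714 + 0.0000314)/1.02195 = 0.0718. The interval is 33.0% to 47.4%, the printed example.
- n = 50, p = 0.40: centre = 0.43842/1.07683 = 0.4071; half-width = 1.96 × √(0.0048 + 0.00038416)/1.07683 = 0.1311. The interval is 27.6% to 53.8%, half-width 13.1 points. Rounded down, this is the printed 13.

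Agresti-Coull agrees with Wilson to the printed precision. So 7.2.4 is consistent with one Wilson-type calculation rounded to whole points.

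**Step 2: apply the planned method.** The Clopper-Pearson limits for x responders in n are the 2.5% quantile of Beta(x, n−x+1) and the 97.5% quantile of Beta(x+1, n−x).

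| n | Responders | Clopper-Pearson 95% | Below | Above | Half-width |
|---|---|---|---|---|---|
| 50 | 20 | 26.4% to 54.8% | 13.6 | 14.8 | 14.2 |
| 125 | 50 | 31.3% to 49.1% | 8.7 | 9.1 | 8.9 |
| 175 | 70 | 32.7% to 47.7% | 7.3 | 7.7 | 7.5 |

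**Step 3: worst case over all observed response rates.**

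| n | Stated | Largest half-width | Longest arm |
|---|---|---|---|
| 50 | 13 | 14.5 | 14.8 |
| 125 | 9 | 9.07 | 9.16 |
| 175 | 8 | 7.64 | 7.69 |

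For n = 50 the half-width exceeds 13 points at every observed ORR from 28% (14/50) to 72% (36/50).

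**Step 4: comparison inside the protocol.** The expansion-cohort examples in Section 7.2.2.1, which names Clopper-Pearson, do reproduce with that method at 80%: 5/30 gives 8.3% to 28.7%, 9/30 gives 19.0% to 43.2%, 15/30 gives 37.0% to 63.0% and 21/30 gives 56.8% to 81.0%. Section 7.2.4 is the one that departs.

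**Step 5: the zero-event statement.** For 0/175 the upper limits are 1 − 0.05^(1/175) = 1.70% (exact, one-sided), 1 − 0.025^(1/175) = 2.09% (exact, two-sided) and z²/(n + z²) = 3.8416/178.8416 = 2.15% (Wilson). All lie below 2.2%.

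**The case against.** The best defence is that 7.2.4 is a planning illustration, coherent in itself. Its figures follow from one Wilson-type method rounded to whole points: at 40% the half-widths for 50 patients are 13.1 (Wilson and Agresti-Coull) and 13.3 (Jeffreys), all of which round to 13. Section 7.9 governs how observed rates are presented, not how planning examples were computed. The cohort size is approximate, and the primary ORR uses only patients with measurable disease by central review, so the final denominators may differ anyway. No threshold, test or stopping rule uses these intervals.

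Most of that stands, and it limits the severity. It does not make the +/-13% describe the interval that will be reported, because 7.2.4 names no method and the only ORR interval the protocol names is Clopper-Pearson. Fewer patients with measurable disease would widen the interval further.

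A reader might infer four stronger things that the documents do not support:

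- *That +/-13% fails under every usual method.* Wald gives 13.6 at 40%, but the Wilson, Agresti-Coull and Jeffreys half-widths round to 13.
- *That it fails for observed rates from 16% to 84%.* That range uses the longer arm of an asymmetric interval. On half-width, the usual reading of +/-, the range is 28% to 72%.
- *That +/-9% for 125 patients is also wrong.* At 40% the half-width is 8.9. The worst excess on either measure is under 0.2 points and disappears on rounding.
- *That the 2.2% bound is an error.* An upper statement that is not the tightest available is still true.

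**Conclusion.** The point holds for two figures in Section 7.2.4. The 50-patient precision is understated relative to the planned method: at 40% the half-width is 14.2 points rather than 13, at most 14.5 over all rates, and the longer arm reaches 14.8. A bound that covers both arms is therefore +/-15%. The 175-patient example is the wrong interval for the plan, by about 0.3 points at each limit, though the +/-8% claim itself is met.

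This assumes two-sided 95% intervals, full groups of 50 and 175, and that the Clopper-Pearson method of 7.9 applies to the extension ORR, as its placement under Tumour response indicates. The severity is low: no decision rule, sample size or analysis depends on the figures, and the reported interval will be Clopper-Pearson whatever 7.2.4 illustrates. It is still worth correcting, because the paragraph is part of the sizing rationale for the primary endpoint.

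**What to change.** In Section 7.2.4:

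- Name Clopper-Pearson as the method behind the precision figures.
- Restate the 50-patient precision as within +/-15%, with the example 26.4% to 54.8% at an ORR of 40%.
- Replace the 175-patient example with 32.7% to 47.7%.

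Leave the +/-8%, the +/-9% and the zero-event statement as they are. The cost is an edit to one paragraph and a slightly less favourable stated precision for the TKI-only group.

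### The ±13% ORR precision stated for the 50-patient TKI-only group is tighter than the planned Clopper-Pearson interval gives (about ±14.5%), and the 175-patient example interval is a Wilson interval

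*Protocol*

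**What the plan says.** Section 7.2.4 makes ORR the primary endpoint of the extension and divides about 175 patients into two groups by prior treatment: "following either one prior therapy with an EGFR-TKI (chemotherapy-naïve, n=50") and "following treatment with both EGFR-TKI and other anti-cancer therapy (n=125"). It gives three precision figures. For the whole cohort, precision "will be within +/-8% (e.g. ORR 40%, 95% CI 33.0%, 47.4"%). For the TKI-only group: "The precision of the estimation of ORR will be within +/-13% in the 50 patient cohort". For the group with further prior therapy: "within +/-9% in the 125 patient cohort". The section names no interval method, and 40% is the only ORR it mentions.

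Section 7.9 fixes the method for the analysis: "Objective tumour response rates will be presented together with 80% and 95% confidence intervals (calculated using the Clopper-Pearson interval), where appropriate". It also says that extension results are summarised overall and separately for the two prior-treatment groups, so the 50-patient and 125-patient intervals will both be reported. Section 7.2.2.1 names Clopper-Pearson for the expansion cohorts too.

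**The concern.** A precision statement in a sample-size section tells the reader how wide the reported interval will be, so it should be calculated with the interval the analysis will use. Here the printed example does not match the planned method, and the 50-patient figure looks too small for an exact interval near the middle of the range. For ORR, Section 7.2.4 offers estimation precision rather than a hypothesis test or power, and ±13% is the only ORR sizing statement for the TKI-only group. If it is wrong, the interval reported for that group will be wider than the protocol said at many response rates.

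**Working it through.** **Inputs.** n = 175, 50 and 125; claims of ±8, ±13 and ±9 points; example ORR 40% with limits 33.0% and 47.4% (all Section 7.2.4). Two-sided 95% Clopper-Pearson (Section 7.9). z = 1.96. Precision is read as the half-width, (upper − lower)/2.

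**Formulas**, with x responders and p = x/n:
- Clopper-Pearson: lower = 2.5% quantile of Beta(x, n−x+1); upper = 97.5% quantile of Beta(x+1, n−x).
- Wilson: [p + z²/(2n) ± z·√(p(1−p)/n + z²/(4n²))] / (1 + z²/n).
- Wald: p ± z·√(p(1−p)/n).

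**Step 1: reproduce the printed example (70/175).**
- Wilson centre: (0.4 + 0.010976)/1.021952 = 0.4021.
- Wilson half-width: 1.96·√(0.24/175 + 3.8416/122,500)/1.021952 = 0.0718.
- Wilson limits: 33.03% and 47.40%, which match the printed 33.0% and 47.4%.
- Clopper-Pearson: 32.68% and 47.66%. Wald: 32.74% and 47.26%. Neither matches.

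Agresti-Coull and logit intervals also round to the printed limits, but none of these is the planned method. By contrast, the four 80% examples for n = 30 in Section 7.2.2.1 do reproduce with Clopper-Pearson (for instance 5/30: 8.3% to 28.7%).

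**Step 2: the 50-patient figure against 13 points.**

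| Observed | Clopper-Pearson 95% | Half-width, Clopper-Pearson | Half-width, Wald | Half-width, Wilson |
|---|---|---|---|---|
| 20/50 (40%) | 26.4% to 54.8% | 14.21 | 13.58 | 13.11 |
| 25/50 (50%) | 35.5% to 64.5% | 14.47 | 13.86 | 13.36 |
| 30/50 (60%) | 45.2% to 73.6% | 14.21 | 13.58 | 13.11 |

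By hand at 25/50:
- Wald: 1.96·√(0.25/50) = 0.1386.
- Wilson: 1.96·√(0.005 + 0.00038416)/1.076832 = 0.1336.

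Over all counts, the Clopper-Pearson half-width is 12.86 at 13/50 (26%) and 13.13 at 14/50 (28%). It stays above 13 up to 36/50 (72%) and is back to 12.86 at 37/50. Its maximum is 14.47. The Wilson half-width exceeds 13 only from 20/50 to 30/50.

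**Step 3: the other two figures under Clopper-Pearson.**
- n = 175: half-width 7.49 at 40%, maximum 7.64. ±8% holds.
- n = 125: half-width 8.90 at 40% (50/125: 31.3% to 49.1%), maximum 9.07. ±9% holds to rounding.

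**The case against.** The best defence is that Section 7.2.4 gives whole-number planning figures for an approximate cohort size and names no method. Planning with Wilson and analysing with Clopper-Pearson is common. If Wilson was used, the 50-patient half-width at 40% to 60% misses 13 by only 0.1 to 0.4 points and rounds to 13. The main estimate, from 175 patients, keeps its ±8%, and Section 7.9 fixes the reported interval whatever Section 7.2.4 says.

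Most of this stands, and it is why the point is minor. It does not clear the figure. The text says within, which states a bound. The companion figures fit Wilson only if rounded up (maximum half-widths 7.33 given as 8 and 8.63 given as 9); the same convention makes 13.36 into 14. Against the planned method the gap is 1.2 to 1.5 points at 40% to 60%, which is more than rounding.

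A reader might infer more than this, and the documents do not support it:
- **That ±9% for 125 patients is also wrong.** It is exceeded by more than rounding only if precision means the distance to the further limit (up to 9.16). By half-width the maximum is 9.07.
- **That the 50-patient claim fails from 16% to 84%.** That range also uses the distance to the further limit. By half-width, the usual meaning of a ± figure, it is 28% to 72%.
- **That ORR precision is the extension's only sizing argument.** The same paragraph also gives a zero-event safety bound of 2.2% for 175 patients.

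**Conclusion.** The ±13% for the 50-patient group is not what the planned analysis delivers. The Clopper-Pearson half-width is 14.2 points at 40% and at most 14.5, and it exceeds 13 for observed ORRs from 28% to 72%. The 175-patient example follows a different method, with each limit about 0.3 points from the Clopper-Pearson value. The other two precision figures stand.

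This rests on reading precision as half-width at two-sided 95%, and on exactly 50 patients in the group. The protocol states no expected ORR for this group, so how likely the result is to fall between 28% and 72% is left open; the paragraph's own 40% lies inside.

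It would be tempting to conclude that the extension is undersized. The protocol does not support that: no test, success threshold or enrolment number depends on ±13%. This is a minor correction to a stated figure.

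**What to change.** Restate Section 7.2.4 on the Clopper-Pearson method and name it there:
- n = 175: keep within ±8%, and change the example at 40% to 32.7% to 47.7%.
- n = 50: about ±14.5%, or within ±15% (at 40%: 26.4% to 54.8%). The within ±15% wording also covers the distance to the further limit, at most 14.83 points.
- n = 125: ±9% can stay, described as a rounded half-width (at 40%: 31.3% to 49.1%).

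The cost is wording only. The stated precision for the TKI-only group becomes slightly less favourable; enrolment, the analysis method and decision rules do not change.

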7.3 Calculation or derivation of safety variables

Safety and tolerability will be assessed in terms of AEs, laboratory data, vital signs, ECG changes. These will be collected for all patients. Appropriate summaries of these data will be presented as described in Section 7.9.

ECG Changes

QTc will be calculated by AstraZeneca using both Bazett's and Fridericia's formulae.

Creatinine Clearance

Estimated creatinine clearance will be calculated using the Cockcroft and Gault formula.

7.3.1 Other significant adverse events

During the evaluation of the AE data, an AstraZeneca medically qualified expert will review the list of AEs that were not reported as SAEs and AEs leading to discontinuation of investigational product. Based on the expert's judgement, adverse events of particular clinical importance may, after consultation with the Global Safety Physician, be considered other significant adverse events (OAEs) and reported as such in the Clinical Study Report. A similar review of laboratory values, vital signs, ECGs and other safety assessments will be performed for identification of other significant adverse events.

Examples of these are marked haematological and other laboratory abnormalities, and certain events that lead to intervention (other than those already classified as serious), dose reduction or significant additional treatment.

7.4 Calculation or derivation of pharmacokinetic variables

Pharmacokinetic analysis of the plasma concentration data for AZD9291 and its metabolites will be performed by

The actual sampling times will be used in the parameter calculations and PK parameters will be derived using standard non-compartmental methods.

Where possible the following PK parameters will be determined for AZD9291.

Following the single dose part (or first dose) of the study:

Maximum plasma concentration (C_{max}), time to C_{max} (t_{max}), terminal rate constant (λ_z), terminal half life ($t_{\nu_2\lambda_z}$), area under the plasma concentration-time curve from zero to 24 hours (AUC₍₀₋₂₄₎), from zero to the time of the last measurable concentration (AUC_(0-t)) and from zero to infinity (AUC), apparent plasma clearance (CL/F), apparent volume of distribution, mean residence time (MRT).

Following the multiple dose part of the study:

Maximum plasma concentration at steady state ($C_{ss max}$), time to $C_{ss max}$ ($t_{ss max}$), minimum plasma concentration at steady state ($C_{ss min}$), area under the plasma concentration-time curve from zero to the end of the dosing interval (AUC_{ss}), apparent plasma clearance at steady state (CL_{ss}/F), extent of accumulation on multiple dosing (R_{AC}), time dependency of the pharmacokinetics.

The maximum plasma concentration (C_{max}), the C_{max} at steady state ($C_{ss\ max}$), the time of maximum concentration (t_{max}) and the t_{max} at steady state ($t_{ss\ max}$) will be determined by inspection of the concentration-time profiles. Where possible the terminal elimination rate constant (λ_z) will be calculated by log-linear regression of the terminal portion of the concentration-time profiles where there are sufficient data and the terminal half-life ($t_{/_2\lambda z}$) will be calculated as $\ln 2/\lambda_z$. The area under the concentration-time curve up to the last quantifiable sample (AUC_(0-t)) and the area under the concentration-time curve up to 24 hours (AUC₍₀₋₂₄₎) will be calculated using the linear trapezoidal rule. Where appropriate, the AUC₍₀-

t) will be extrapolated to infinity using $λ_z$ to obtain AUC. The area under the concentrationtime curve across the dosing interval, AUC_{ss} will be calculated using the linear trapezoidal rule. The apparent clearance (CL/F following the single dose and CL_{ss}/F following multiple dosing) will be determined from the ratio of dose/AUC or dose/AUC_{ss}. The volume of distribution (V_{ss}/F or V_z/F) will be determined from the mean residence time (MRT) x CL/F and/or the accumulation ratio (R_{AC}) will be calculated as the ratio of the AUC₍₀₋₂₄₎ on Day 15 and Day 1. The time dependency of the pharmacokinetics on multiple dosing will be assessed by the calculation of the ratio of AUC₍₀₋₂₄₎ Day 15/AUC Day 1.

Where possible the appropriate pharmacokinetic parameters will also be determined for the metabolites of AZD9291.

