5. STUDY TREATMENT AND CONDUCT

5.1 Treatment

AZD9291 is planned to be administered orally as a single daily dose (although alternative frequencies or intermittent schedules may be instigated in response to emerging safety, tolerability or PK data).

AstraZeneca will supply AZD9291 as capsules or tablets for oral dosing. Additional information about the investigational product may be found in the Investigators' Brochure.

Investigational product	Dosage form and strength	Manufacturer
AZD9291	20 mg and 40 mg Capsule	AstraZeneca
AZD9291	40mg and 80mg Tablet	AstraZeneca

Capsules and tablets will be packed in high-density polyethylene (HDPE) bottles with childresistant closures. One or more bottles of AZD9291 will be dispensed at each dispensing visit depending on the dose. Bottles will be dispensed to subjects in the AstraZeneca packing provided. The packaging includes bottles, caps and a label. Bottle tampers should not be broken prior to dispensing study drug to a patient. For the Ph II extension cohort an IVRS/IWRS system will be deployed to manage the supply of AZD9291 tablets to sites and to manage the dispensing of AZD9291 to patients. All patients entering the extension cohort will be dispensed the tablet formulation. All other cohorts of patients will continue to be dispensed the capsule formulation.

Labels will be prepared in accordance with Good Manufacturing Practice and local regulatory guidelines. The labels will fulfil Good Manufacturing Practice Annex 13 requirements for labelling. Label text will be translated into local language.

The label will include the Name of the Sponsor, Study Code, For Clinical trial use only and /or any other market specific requirements

All study drugs should be kept in a secure place under appropriate storage conditions. The investigational product label on the pack specifies the appropriate storage.

Patients (with the exception of patients with insulin dependent diabetes) must fast for ≥ 1 hours prior to taking a dose to ≥ 2 hour post dose. Water is permitted during this fasting period.

Patients will be required to fast (water only) for at least 8 hours prior to the collection of a fasting glucose sample as per the study plan, (see Table 2, Table 3 and Table 4).

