Plasma concentrations of AZD9291, AZ5104 and AZ7550 will be summarised by nominal sample time. Plasma concentrations and derived PK parameters will be summarised by dose level. Parameters following single and multiple dosing will be summarised separately. Plasma concentrations at each time point will be summarised according to dose by the following summary statistics:

- The geometric mean (gmean, calculated as $\exp [\mu]$, where μ is the mean of the data on a logarithmic scale)
- Coefficient of variation (CV, calculated as $100 \sqrt{[exp(s^2)-1]}$, where s is the standard deviation of the data on a log scale)
- Gmean \pm standard deviation (calculated as exp[$\mu \pm s$])
- Arithmetic mean calculated using untransformed data
- Standard Deviation calculated using untransformed data
- Minimum
- Maximum
- Number of observations

The following summary statistics will be presented for AUC, AUC₍₀₋₂₄₎, AUC_(0-t), AUC_{ss}, C_{max} , $C_{ss max}$ and $C_{ss min}$:

- Gmean, calculated as $exp[\mu]$, where μ is the mean of the data on a logarithmic scale)
- CV, calculated as $100 \sqrt{[\exp(s^2)-1]}$, where s is the standard deviation of the data on a log scale)
- Arithmetic mean calculated using untransformed data
- Standard deviation calculated using untransformed data
- Minimum
- Maximum
- Number of observations

The following summary statistics will be presented for CL/F, CL_{ss}/F, volume of distribution, $t_{1/2\lambda z}$, R_{AC} , time dependency:

Revised Clinical Study Protocol Drug Substance AZD9291 Study Code D5160C00001 Edition Number 3 Date

- Arithmetic mean
- Standard deviation
- Minimum
- Maximum
- Number of observation

The following summary statistics will be presented for t_{max} and t_{max ss}:

- Median
- Minimum
- Maximum
- Number of observations

The pharmacokinetic data for AZD9291, AZ5104 and AZ7550 after a single-dose and separately, at steady state will also be displayed graphically. Displays will include plasma concentration patient profiles (on the linear and log-scale) versus time and gmean concentration (+/-standard deviation) versus time, stratified by dose.

Scatter plots of PK parameters versus dose, or log-dose will also be considered following both single and multiple dose administration of AZD9291 to assess dose proportionality.

In a preliminary assessment of dose proportionality, log-transformed AUC and C_{max} parameter estimates will be examined using the Power Model:

parameter = $e^a (dose)^b$

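### After oral dosing the stated volume formula, MRT × CL/F, overstates Vss/F, and the sentence breaks off without giving a usable formula for Vz/F

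*Protocol*

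**What the plan says.** Section 5.1 sets the route: "AZD9291 is planned to be administered orally as a single daily dose". The protocol has no intravenous arm. Section 7.4 states that "PK parameters will be derived using standard non-compartmental methods" and lists, among the single-dose parameters, "apparent plasma clearance (CL/F), apparent volume of distribution, mean residence time (MRT"). That list does not say which volume is meant.

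The only derivation of a volume comes later in Section 7.4, where it "will be determined from the mean residence time (MRT) x CL/F". In context the sentence reads: "The volume of distribution (V_{ss}/F or V_z/F) will be determined from the mean residence time (MRT) x CL/F and/or the accumulation ratio". From there the sentence goes straight on to define the accumulation ratio. No correction of MRT for absorption is mentioned, and no other volume formula appears in the protocol.

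The same section does derive what Vz/F needs. The terminal rate constant λz "will be calculated by log-linear regression of the terminal portion of the concentration-time profiles where there are sufficient data", and single-dose CL/F is dose divided by AUC. Section 7.9 then carries one unspecified volume into the tables: "The following summary statistics will be presented for CL/F, CL_{ss}/F, volume of distribution". The abbreviation list defines Vss/F but not Vz/F.

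**The concern.** Two things are wrong with the volume sentence.

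First, MRT × CL/F gives the steady-state volume only when MRT is the residence time of drug already in the circulation, as after an intravenous bolus. After an oral dose, the non-compartmental MRT also counts the time the drug spends being absorbed. Multiplying by CL/F turns that extra time into extra apparent volume. The error has a fixed direction (upward) and grows as absorption slows relative to elimination.

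Second, Vss/F and Vz/F are different quantities, and the sentence offers them as alternatives with one formula and a dangling connective. An analyst following it has no stated route to Vz/F, and a reader of the tables cannot tell which volume is shown.

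At stake is the correctness and labelling of one descriptive parameter under the secondary objective of characterising the pharmacokinetics.

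**Working it through.** **Inputs from the protocol.** Oral dosing only (5.1); non-compartmental methods, CL/F = dose/AUC, λz by log-linear regression, and volume from MRT × CL/F (7.4); volume summarised descriptively (7.9). The plan gives no numerical figure for volume, so there is none to reproduce.

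**Step 1: what the formula returns.** Non-compartmental MRT is AUMC/AUC. After an oral dose:

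MRT(oral) = MRT(iv) + MAT

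Since Vss/F = MRT(iv) × CL/F,

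MRT(oral) × CL/F = Vss/F + MAT × CL/F

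and the relative overstatement of Vss/F is MAT/MRT(iv). By contrast, Vz/F = (CL/F)/λz.

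**Step 2: numerical check.** AUMC/AUC was computed on simulated oral profiles with F = 1 and CL = 10. Volume units are arbitrary and all parameter values are assumed.

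| Model | MAT (h) | Half-life (h) | Vss | Vz | MRT × CL/F | Vss + MAT × CL |
|---|---|---|---|---|---|---|
| One-compartment | 4 | 20.8 | 300 | 300 | 340 | 340 |
| Two-compartment | 2 | 23.7 | 200 | 341 | 220 | 220 |
| Two-compartment | 2 | 84.4 | 300 | 1218 | 320 | 320 |
| Two-compartment | 4 | 22.1 | 300 | 319 | 340 | 340 |

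The last two columns agree in every case. The overstatement of Vss is 40/300 = 13%, 20/200 = 10%, 20/300 = 7% and 40/300 = 13%. Against Vz the formula has no fixed direction: it is above Vz in the first and fourth rows and far below it in the second and third.

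**Step 3: plausible size.** In a one-compartment model MRT(iv) = half-life/ln 2, so the overstatement is MAT × ln 2/half-life. The documents give neither quantity, so this is a range over assumed values:

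| Half-life (h) | MAT 1 h | MAT 2 h | MAT 4 h | MAT 6 h |
|---|---|---|---|---|
| 12 | 6% | 12% | 23% | 35% |
| 24 | 3% | 6% | 12% | 17% |
| 34 | 2% | 4% | 8% | 12% |
| 48 | 1% | 3% | 6% | 9% |

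The 34 h row is the only one with any anchor in the protocol. The cardiovascular part of Section 5.3.2 presumes steady state at Day 8 of continuous dosing, that is, after about 7 days. Assuming that five half-lives are needed, 168 h/5 ≈ 34 h. If absorption is instead described by a tmax of 2 to 8 h, solving tmax = ln(ka/ke)/(ka − ke) for ka at that half-life gives an overstatement, ke/ka, of about 1 to 5%. Taking both descriptions together, the range at 34 h is about 1 to 12%.

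**Step 4: the broken sentence.** It opens with two volumes, gives one product, reaches the connective, and then continues with the accumulation ratio as the ratio of two AUCs. The accumulation ratio is not a route to a volume, so the words after the connective cannot be the second volume expression. Something is missing between the two.

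**The case against.** **The gap may hide the right formula.** A sentence that names two volumes probably had two expressions, and the second may have been lost in drafting or in conversion of the file. This stands. A reader might infer that the protocol prescribes MRT × CL/F for Vz/F; the text does not establish that. What can be said is that, as the sentence reads, no usable Vz/F formula is given. Whatever was lost does not repair the Vss/F part, which is complete as it stands.

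**Vss/F can be estimated in other ways.** A reader might infer that this study cannot estimate Vss/F at all. That goes too far. Section 7.5.1 plans a population PK analysis of the same concentrations, and such a model can include an absorption process and estimate apparent volumes, subject to identifiability. The limitation applies to the non-compartmental parameter of Section 7.4, which the population analysis does not correct.

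**The bias may be small.** This stands as a possibility. Overstatements of 25% or more need a short half-life with slow absorption (for example 12 h with a tmax of 8 h, or with a MAT of 6 h), and nothing in the documents supports that pairing. The presumed steady state at Day 8 points to a longer half-life, though a presumption about steady state bounds the half-life only loosely.

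**Vz/F is not a corrected Vss/F.** This also stands. In the two-compartment examples Vz is 341 against a Vss of 200, and 1218 against 300. Reporting Vz/F changes the quantity, and the tables must say so.

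**Little depends on it.** Correct. Dose proportionality uses AUC and Cmax, and no stated decision rule refers to volume.

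**Conclusion.** The point holds, at minor severity. Followed as written for an oral-only study analysed non-compartmentally, the formula in Section 7.4 yields Vss/F + MAT × CL/F and so overstates Vss/F. That direction does not depend on any assumed value. The size does: about 1 to 12% for a half-life near 34 h under a one-compartment model with MAT of 1 to 6 h or tmax of 2 to 8 h, and more if the half-life is shorter. The 34 h value rests on the presumed steady state at Day 8 and on an assumed five half-lives to reach it.

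Separately, the volume sentence is incomplete, states no usable Vz/F formula, and leaves open which volume Sections 7.4 and 7.9 will list and summarise. The consequence is confined to a descriptive PK summary; no endpoint, stated dose-escalation rule, sample size or error rate uses the volume.

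**What to change.** In Section 7.4:

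- Check the source file for text lost after the connective, and complete the sentence by defining the reported non-compartmental volume as Vz/F = (CL/F)/λz, which after a single dose equals dose/(AUC × λz).
- Either drop MRT × CL/F or, if it is kept, label it as including absorption time and do not call it Vss/F. MRT itself can stay as a descriptive parameter with the same note.
- Put the accumulation ratio in a sentence of its own.

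Then replace the unspecified volume with Vz/F in the single-dose parameter list of Section 7.4 and in the summary statistics of Section 7.9, and add Vz/F to the abbreviation list.

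The cost is a few lines of text. CL/F and λz are already derived, so no new samples or assessments are needed. As Section 7.4 already allows for λz, Vz/F will be available only for profiles with enough terminal data.
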